#### Interim analysis for OS tests

Regardless of PFS results, the first interim analysis of OS will be performed at the final PFS analysis time (expected to be 24 months after study activation-see Section [9.2.1](#)). Interim analysis for OS will then be performed biannually until either the criteria for early stopping (described below) are met or the total planned number of OS events has been reported. Of note, interim analyses will be skipped if the change in the information since the previous interim analysis is less than 10%. In addition, when the information time reaches 90% or more, interim analysis will not be conducted, and the final analysis of OS will be performed when full information is reached. These interim analyses will be monitored by ECOG-ACRIN DSMC. Table 9.2 shows the operating characteristics for OS endpoint.

At each interim analysis, the stratified log rank test statistic will be computed. To preserve the overall one-sided type I error rate at 2.4% for the OS endpoint, critical values for rejecting null hypothesis at the interim analyses will be determined using a truncated version of the Lan-DeMets spending function corresponding to the O'Brien-Fleming boundary (1979). If the boundary is crossed at an interim analysis or at the final analysis, then the null hypothesis will be rejected, and the Exemestane + Entinostat therapy is superior to the exemestane monotherapy in terms of OS. If the criteria for rejecting the null hypothesis are not met, then it will be concluded that this trial fails to show superiority of Exemestane + Entinostat therapy over the exemestane monotherapy on OS.

Because interim analyses are timed to coincide with the ECOG-ACRIN DSMC meetings, these boundaries may change depending on the number of observed OS events at that time. Also, because of

delays in data submission and processing, it is likely that actual analysis times will be 6-12 months later.

**Table 9.2: Operating Characteristics for OS Endpoint**

Repeated Analysis	Real time (months)	Information time	Failures under alternative hypothesis	Nominal significance (one-sided)	Upper boundary
1	24	0.24	101	0.00048	3.3020
2	30	0.36	149	0.00048	3.3020
3	36	0.49	203	0.00068	3.2036
4	42	0.64	261	0.00400	2.6518
5	48	0.76	313	0.00805	2.4065
6	54	0.87	355	0.01193	2.2593
Final	64	1.00	410	0.01872	2.0808

If PFS test is negative in the primary analysis, this study will also be monitored for early stopping in favor of the null hypothesis (i.e., futility) for the OS test using the Jennison-Turnbull repeated confidence interval (RCI) method. At each interim OS analysis, the RCI on the observed hazard ratio will be computed using the critical values from the above error spending rate function. If the RCI does not include the alternative hazard ratio of 1.33 (arms B/A), then the OS comparison would be stopped early for lack of benefit. The observed hazard ratio will be calculated using stratified Cox proportional-hazards model, stratified on randomization stratification factors, without any other covariates. If the PFS test is positive in the primary analysis, no interim futility analysis for OS will be conducted.

As mentioned in Section 9.2.1, if the first interim analysis of OS is positive, the interim OS data will be released to Syndax and the public and the study will be stopped early for efficacy. If the first interim analysis of OS does not cross the efficacy boundary, then at the time study accrual is completed, if (1) the primary PFS test is positive at the 0.001 level, and (2) the estimated PFS hazard ratio for Exemestane + Entinostat vs. Exemestane + Placebo is  $< 0.675$ , the interim OS data will also be confidentially released to Syndax. The DSMC will also be asked to allow use of interim OS data from the first 360 patients enrolled in an application to the FDA, with the understanding that the data not be made public unless required as part of the FDA review process.

**Interim analysis for toxicity**

For safety considerations, an interim analysis for toxicity data will be conducted when 30 patients have been assigned to arm A and have received at least one dose (expected to occur at about 4 months after study activation). If more than 6 Grade 4 non-hematologic toxicity

events (at a rate of 20%) are observed in the first 30 patients in this arm, the study will be terminated. Table 9.3 shows the probability that the trial will be terminated early due to excessive toxicity. This probability is provided under different assumptions about the true proportion of Grade 4 non-hematologic toxicity in this arm.

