### 9.2 Study Design

Patients with histologic confirmation of invasive adenocarcinoma of the breast will be randomized according to the permuted block algorithm with a 1:1 randomization ratio to arms A and B. Stratification factors include:

- Setting in which patient developed resistance to prior non steroidal AI treatment (adjuvant vs. metastatic)
- Geographic region (USA vs. other)
- Visceral disease (yes vs. no)
- Prior fulvestrant use (yes vs. no)

**NOTE:** Visceral disease is defined as lung and/or liver involvement.

Taking into consideration the accrual rates of the BOLERO-2 study (40 patients/month, 700 patients over 18 months with 24 international sites), the ENCORE 301 study (5 patients/month, 130 patients over 2 years at 38 sites US and international) and the CONFIRM study (24 patients/month at 128 sites), all of which have been conducted in the AI refractory setting, and the 1st line SWOG

S0226 study (10 patients/month, 700 patients over 6 years), we anticipate an accrual rate of approximately 15 patients per month in our study.

Enrollment of 600 patients will be required to provide adequate power for the OS endpoint (see Section [9.2.2](#)). The first 360 patients will be used for the primary evaluation of PFS (see Section [9.2.1](#)), objective response rate (ORR), toxicity, time to treatment deterioration and patient-reported outcomes. If the PFS analysis is positive, the data for first 360 patients would be used for a submission to the FDA. At the time of final analysis for the OS endpoint, secondary analyses of PFS, objective response and toxicity will be conducted in all 600 patients, along with the primary analyses for the pharmacodynamic acetylation marker data and adherence to protocol therapy data. Imaging studies for all 600 participants will be collected and archived at the ACR Imaging Core Laboratory.

For purposes of comparability to the phase 3 study of exemestane in advanced breast cancer patients by Chia et al., enrollment in this study will attempt to achieve a target patient population that consists of approximately 80% of patients having measurable disease (with at least 1 measurable lesion at baseline assessment and identification of up to 5 total target lesions [maximum of 2 lesions per organ] and 5 total non-target lesions) and approximately 20% of patients having non-measurable disease only.

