**Table 9.3: Probability that the trial will be terminated early due to excessive toxicity on arm A**

True proportion of the toxicity	0.10	0.15	0.20	0.25	0.30	0.35
Probability of early termination	0.026	0.15	0.39	0.65	0.84	0.94

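### The arm A toxicity look has no minimum follow-up, so Table 9.3 holds only for toxicity already seen at the look; for a cycle-1 or longer rate the chance of stopping is lower, unless essentially all onset is at the first dose

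*Combined protocol and SAP*

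**What the plan says.** Section 9.2, under the heading on interim analysis for toxicity, sets one look at Grade 4 non-hematologic toxicity on arm A. It takes place "when 30 patients have been assigned to arm A and have received at least one dose", and this is "expected to occur at about 4 months after study activation". The stopping condition opens "If more than 6 Grade 4 non-hematologic toxicity" and refers to events in the first 30 patients on that arm; if it is met, the study is terminated. No minimum follow-up, observation window or data cut-off is given for this look.

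Table 9.3 gives the "Probability that the trial will be terminated early due to excessive toxicity on arm A" as 0.026, 0.15, 0.39, 0.65, 0.84 and 0.94 at true proportions 0.10, 0.15, 0.20, 0.25, 0.30 and 0.35. The text says of the table: "This probability is provided under different assumptions about the true proportion of Grade 4 non-hematologic toxicity in this arm". It does not say whether that proportion is by the look, in cycle 1 or over the whole treatment period.

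Section 9.2 also supplies the pace of enrolment: "we anticipate an accrual rate of approximately 15 patients per month in our study", "with a 1:1 randomization ratio to arms A and B". Under Section 5.1, cycles last 28 days and repeat until progression or unacceptable toxicity. In the Section 7 calendar, symptom and toxicity assessments after baseline fall at the end of each cycle; the Cycle 1 Day 15 visit has only blood counts, chemistries and research samples.

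**The concern.** The trigger counts patients who have started treatment, not patients who have been observed. The table, however, gives each of the 30 patients the full probability p of having had the event. The two agree if p means toxicity that has appeared by the look. They do not agree if p is read as a property of the regimen, such as the proportion affected in cycle 1 or during treatment, unless essentially all onset is at the first dose.

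The second reading is the one most users of the table will adopt, because the row label names a true proportion with no time limit and Section 9.4 summarises toxicity by worst grade among treated patients. A monitoring committee that takes 0.84 as the chance of stopping at a 30% rate may then be relying on more protection than a count at the trigger gives.

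**Working it through.** **Inputs.** Accrual 15 per month and 1:1 allocation (Section 9.2), so 7.5 arm A patients per month. Threshold more than 6, that is at least 7, of 30 (Section 9.2). Cycle length 28 days (Section 5.1), or 28/30.44 = 0.92 months. Assumed, because the documents do not give them: even accrual, treatment starting at randomization, at most one event counted per patient, and the onset patterns below.

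**Step 1: reproduce Table 9.3.** With X ~ Binomial(30, p), P(X ≥ 7) at p = 0.10, 0.15, 0.20, 0.25, 0.30, 0.35 is 0.0258, 0.1526, 0.3930, 0.6519, 0.8405, 0.9414. All six entries match the table. It is the exact binomial tail with every patient fully observed for p.

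**Step 2: exposure at the trigger.** Time to enrol 30 arm A patients is 30/7.5 = 4.0 months, equal to the stated time of the look, so nothing is added for follow-up. Patient i has had e_i = (30 − i)/7.5 months on treatment. The mean is 1.93 months. Completed cycles: 23 of 30 patients have finished at least one, 16 at least two and 9 at least three. The other 7 have not reached their first scheduled on-treatment symptom and toxicity assessment.

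**Step 3: chance of stopping at the trigger.** If onset is uniform over k cycles, patient i has shown the event with probability q_i = p × min(1, e_i/(0.92k)). The chance of stopping is the exact probability that the sum of 30 independent indicators with probabilities q_i is at least 7.

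| Onset pattern (assumed) | Mean fraction of p observed | Expected patients with event, p = 0.30 | p = 0.10 | p = 0.20 | p = 0.25 | p = 0.30 |
|---|---|---|---|---|---|---|
| All at first dose (equals Table 9.3) | 1.000 | 9.0 | 0.026 | 0.393 | 0.652 | 0.840 |
| Uniform over 1 cycle | 0.868 | 7.8 | 0.012 | 0.255 | 0.486 | 0.703 |
| Uniform over 2 cycles | 0.753 | 6.8 | 0.006 | 0.151 | 0.329 | 0.536 |
| Uniform over 3 cycles | 0.638 | 5.7 | 0.002 | 0.075 | 0.186 | 0.345 |

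The expected count is 30 × 0.30 × the mean fraction. With two- or three-cycle onset it falls below the 7 needed to stop, although the eventual expectation is 9.

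**Step 4: effect of waiting.** The same calculation with every exposure lengthened, at p = 0.30:

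| Onset pattern (assumed) | At the trigger | 30th patient completes cycle 1 | 30th patient completes cycle 2 |
|---|---|---|---|
| Uniform over 1 cycle | 0.703 | 0.840 | 0.840 |
| Uniform over 2 cycles | 0.536 | 0.778 | 0.840 |
| Uniform over 3 cycles | 0.345 | 0.657 | 0.800 |

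**The case against.** The strongest reply is that nothing in Table 9.3 is wrong. Its arithmetic is exact, and the plan never says that p covers exposure beyond the look. If p is the proportion with an event by the look, nothing is overstated. This stands. A reader might infer that the table is simply overstated, or that the stated safety protection is not delivered; the documents do not support either without a definition of p and an onset pattern. They do show that the definition is missing and that the trigger requires no follow-up.

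Other points against, and what remains of each:

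- **The size depends on an assumed onset.** True. At p = 0.30 it runs from no effect (all onset at the first dose) to 0.35 (three cycles). The direction for a cycle-1 or longer rate does not depend on the exact shape.
- **A single dose describes only the newest patients.** Correct: 23 of 30 have completed a cycle. The calculation uses each patient's own exposure.
- **The rows quoted are high.** Section 9.3.2 plans on a grade 3-4 rate of 24% on arm A, so Grade 4 non-hematologic rates of 25% or 30% would be extreme. But these are the rates the rule exists to catch, and at p = 0.20 the stated 0.39 becomes about 0.26, 0.15 or 0.08.
- **The rule counts events, the table counts patients.** Repeat events in one patient would raise the chance of stopping, so the net direction under a literal event count is not established. This is another reason to define the count.
- **A reporting lag would let toxicity accumulate.** It would shrink the gap, but the 6-12 month lag in Section 9.2 is stated for the PFS and OS analyses, not for this look.
- **There are other safeguards.** The monitoring committee reviews safety twice a year, serious Grade 4 and 5 events need expedited reporting (subject to listed exceptions), and there is an early PFS look for harm. These are real, but none applies this rule or carries the probabilities in Table 9.3.
- **The look has probably passed.** Section 3.1.3 says the quota of patients with non-measurable disease, about 20% of 600, was filled by October 2016. That inference is reasonable. It limits when a recount could act but does not supply the missing definition.

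**Conclusion.** The concern holds in a limited form. The look is triggered by the 30th arm A patient's first dose with no minimum follow-up, so Table 9.3 is valid only for toxicity already observed at that point. For a cycle-1 or longer per-patient rate, the probability of stopping is below the stated figure unless essentially all toxicity occurs at the first dose. Under uniform onset over 1, 2 or 3 cycles with the data cut at the trigger, 0.84 at p = 0.30 becomes about 0.70, 0.54 or 0.35, and 0.65 at p = 0.25 becomes about 0.49, 0.33 or 0.19.

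These figures are illustrations under assumed onset, even accrual and one counted event per patient. The documents fix none of these except the planned accrual rate. This is a gap in the definition of the rule and its operating characteristics, not an arithmetic error.

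**What to change.** Keep the month-4 look and the sponsor's threshold. Add a second application of the same count, more than 6 of the first 30 arm A patients, when the 30th of them has completed cycle 1, or preferably cycle 2. Define the count at both times as patients with at least one Grade 4 non-hematologic toxicity, and state that p in Table 9.3 is the proportion of patients with such a toxicity by the later count.

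No new boundary is needed. The number of affected patients among the same 30 cannot fall, so stopping at either time is the same as having at least 7 at the later one, and the table then gives the overall probability exactly for p so defined. The later count does not capture toxicity arising after it, as the working shows for three-cycle onset.

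The cost is one extra count of data already being collected, 1-2 months after the first, and a slightly higher chance of stopping at a tolerable rate than the month-4 count alone. That chance is no more than the table already states (0.026 at p = 0.10). If the look has already taken place, the count through cycle 1 or 2 in those 30 patients can be taken from data in hand and reported with the definition of p.

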**Expedited 24-hour notification followed by complete report within 5 calendar days for:**

- All Grade 4 and Grade 5 AEs

**NOTE:** Any death occurring greater than 30 days after the last dose of investigational agent with an attribution of possible, probable or definite must be reported via CTEP-AERS even if the patient is off study.

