at diagnosis, prior adjuvant chemotherapy, prior hormonal therapy, et al. The assumption of proportionality in the Cox models will be assessed by investigating the weighted Schoenfeld residuals for each predictor. Patients with missing values for covariates will be excluded from modeling when the proportion of missingness is less than 5% and will be imputed appropriately if the proportion of missingness is  $\geq 5\%$ . ORR will be summarized along with the exact binomial 95% confidence interval and compared between the two arms using Fisher's exact tests.

TTD is defined as time from randomization to disease progression or death or worsening of symptoms, whichever occurs first. All primary analysis for TTD will be based on all cases receiving at least one dose of protocol treatment (i.e., all treated population). The distribution of TTD will be estimated using Kaplan-Meier method, and TTD comparisons between treatment arms will be tested primarily using log-rank test. Cox proportional-hazards models will be conducted to estimate the HR for treatment effect for TTD as a supportive analysis. Same factors included in the multivariable Cox model for PFS and baseline symptom level will be included as predictors for TTD.

Analyses pertaining to toxicity will be based on all treated cases. Adverse events will be graded using the National Cancer Institute (NCI) Common Terminology Criteria for Adverse Events (CTCAE). All treatment-emergent and baseline adverse events and hematological/biochemical toxicities based on laboratory measurements, as well as drug related AE's, will be summarized by treatment group and NCI CTCAE worst grade. The incidence of deaths and treatment-emergent serious adverse events (defined as number of patients experiencing the AE divided by all treated patients) will be summarized and compared between treatment arms using Fisher's exact test. Also, the incidence of adverse events leading to discontinuation of investigational product and/or withdrawal from the study will be summarized and listed.

In all analyses, P-values will be two-sided. A level of 0.2% will be considered statistically significant for stratified log rank test for the primary PFS analysis. For OS comparison, the significance level for stratified log rank test will be 4.8%. For all other tests, a level of 5% will be considered statistically significant.

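### The interim toxicity rule counts Grade 4 events while Table 9.3 counts patients, and a fatal toxicity does not count toward it; the wording should be brought into line with the table

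*Combined protocol and SAP*

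**What the plan says.** The look takes place "when 30 patients have been assigned to arm A and have received at least one dose", expected about 4 months after activation. The rule opens with the threshold: "If more than 6 Grade 4 non-hematologic toxicity". The unit counted and the consequence come in the rest of that sentence: "events (at a rate of 20%) are observed in the first 30 patients in this arm, the study will be terminated". Termination is mandatory under this wording.

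Table 9.3 follows. Section 9.2 introduces it as the chance of stopping under "different assumptions about the true proportion of Grade 4 non-hematologic toxicity in this arm". Its rows are headed "True proportion of the toxicity" and "Probability of early termination". Neither the rule nor the table says that a patient counts once, and neither mentions Grade 5.

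Other parts of the plan are more explicit:

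- The reporting rules in Section 5.2.5.2 name both grades: "All Grade 4 and Grade 5 AEs".
- Section 9.4 gives the incidence of deaths and serious events per patient, "defined as number of patients experiencing the AE divided by all treated patients", and summarises adverse events by worst grade.
- Section 5.2.7 requires expedited reporting of any death on study or within 30 days of the last dose, whatever the cause. It has deaths from progressive disease coded as a Grade 5 event called Disease progression.

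**The concern.** There are two separate gaps between the rule as written and what it appears intended to do.

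The first is the unit. A patient can have several Grade 4 non-hematologic toxicities. Taken literally, each adds one to the count, so a few patients with multiple events could reach seven. The probabilities in Table 9.3 describe a count of patients, in which that cannot happen.

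The second is the grade. A toxicity that kills the patient is Grade 5 and falls outside a rule that names only Grade 4. If the interim tabulation follows the worst-grade convention of Section 9.4, a Grade 4 toxicity that later proves fatal would drop out of the count, and a worse outcome would move the study further from the threshold.

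The rule decides whether a 600-patient trial continues. With a count near seven, two people applying the same sentence could reach opposite decisions.

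**Working it through.** **Inputs.** Section 9.2 gives n = 30 treated arm A patients and a threshold of more than 6, so stopping occurs at 7 or more. Table 9.3 gives true proportions p from 0.10 to 0.35 with their stopping probabilities. The documents give no mean number of Grade 4 events per affected patient and no rate of fatal toxicity; values used for these are assumptions.

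**Step 1: reproduce Table 9.3.** Let X be the number of affected patients, X ~ Binomial(30, p). The stopping probability is P(X ≥ 7) = 1 − Σ(k=0..6) C(30,k) p^k (1−p)^(30−k). At p = 0.10 the sum is 0.9742, so the result is 0.0258.

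| p | Table 9.3 | P(X ≥ 7) | P(X ≥ 6) |
|---|---|---|---|
| 0.10 | 0.026 | 0.0258 | 0.0732 |
| 0.15 | 0.15 | 0.1526 | 0.2894 |
| 0.20 | 0.39 | 0.3930 | 0.5725 |
| 0.25 | 0.65 | 0.6519 | 0.7974 |
| 0.30 | 0.84 | 0.8405 | 0.9234 |
| 0.35 | 0.94 | 0.9414 | 0.9767 |

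All six entries match a count of patients with stopping at 7 or more. A threshold of 6 or more does not match.

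**Step 2: the literal event count.** Take K ~ Binomial(30, p) affected patients, each with 1 + Poisson(m − 1) events, so that m is the assumed mean number of events per affected patient. Stop if total events reach 7. Simulation with 400,000 runs per cell gives:

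| p | m = 1 | m = 1.25 | m = 1.5 | m = 2 |
|---|---|---|---|---|
| 0.10 | 0.026 | 0.115 | 0.217 | 0.403 |
| 0.15 | 0.153 | 0.343 | 0.493 | 0.688 |
| 0.20 | 0.394 | 0.606 | 0.734 | 0.868 |
| 0.25 | 0.652 | 0.807 | 0.886 | 0.953 |
| 0.30 | 0.841 | 0.924 | 0.959 | 0.986 |
| 0.35 | 0.941 | 0.975 | 0.988 | 0.997 |

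A geometric distribution for the extra events gives similar values (0.219 at p = 0.10, m = 1.5). Only m = 1, one event per affected patient, returns the table. Repeat events make stopping more likely than tabulated, never less.

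**Step 3: adding Grade 5.** Let p4 be the proportion of patients with Grade 4 toxicity and p5 the additional proportion whose toxicity is Grade 5 (assumed). The present rule, counting patients, stops with P(X ≥ 7) at p4; a Grade 4–5 rule stops with P(X ≥ 7) at p4 + p5.

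| p4 | p5 (assumed) | Grade 4 only | Grade 4–5 |
|---|---|---|---|
| 0.10 | 0.02 | 0.026 | 0.061 |
| 0.10 | 0.05 | 0.026 | 0.153 |
| 0.15 | 0.05 | 0.153 | 0.393 |
| 0.20 | 0.05 | 0.393 | 0.652 |

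The Table 9.3 figures carry over to the wider rule if p is read as the Grade 4–5 proportion.

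**The case against.** The strongest reply is that patients were plainly meant. The 20% in the rule is 6/30, the table is headed by a true proportion, and its entries are the patient-level binomial. On that reading the operating characteristics are right and one word is loose. This stands. A reader might infer from the wording that Table 9.3 is wrong; the documents do not support that.

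Omitting Grade 5 does not make the table wrong either, because the table is defined for the Grade 4 proportion. One could say that stopping at a 25% rate falls from 0.65 to 0.53 or 0.39 if 10% or 20% of the toxicity is fatal (p = 0.225 or 0.20). That comparison first redefines p as the Grade 4–5 proportion and then subtracts from it. It describes a limit on the rule's scope.

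Nor are toxic deaths unmonitored, which is another tempting inference. Section 5.2.7 requires expedited reporting of deaths, and Section 9.9 has the DSMC review safety twice a year with possible access to unblinded toxicity data. The PFS harm look at 25% information can stop the whole trial, and under Section 9.1 death without progression is a PFS event. All of this stands, but none of it settles which count triggers mandatory termination under the toxicity rule.

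Finally, the look may already be past. Section 3.1.3 records that the quota for non-measurable disease was reached by October 2016. At about 20% of 600 (Section 9.2), that is some 120 patients, more than the roughly 60 randomized patients needed for 30 on arm A. The documents do not state that the look was done, so this remains an inference.

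**Conclusion.** The point holds as a defect of wording and scope. Table 9.3 is correct for a count of patients with Grade 4 toxicity. The rule's text counts events and so matches the table only if no patient has more than one. The text also leaves fatal treatment toxicity out of the plan's only numerical toxicity threshold, although deaths are reviewed by other routes.

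The size cannot be fixed from the documents. Under the literal reading, with an assumed 1.25 to 1.5 events per affected patient, stopping at a true 15% rate would be 0.34 to 0.49 against the tabulated 0.15. The effect of leaving out Grade 5 depends wholly on an unstated fatal rate. These figures illustrate direction and sensitivity; they do not estimate what would happen in this trial.

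**What to change.** In Section 9.2, define the numerator as the number of the first 30 treated arm A patients with at least one Grade 4 or Grade 5 non-hematologic toxicity, each patient counted once. State that deaths coded under Section 5.2.7 as Grade 5 Disease progression are excluded; otherwise, in a metastatic population, deaths from the cancer could be counted as toxicity. Keep the threshold of more than 6 and the figures in Table 9.3. Reword the sentence introducing the table so that its true proportion is the proportion of patients with Grade 4–5 non-hematologic toxicity.

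The cost is a small text change, with no new data and no recalculation. Counting patients once brings the rule back to the tabulated probabilities. Including Grade 5 is a design decision for the sponsor with a small price: at a fixed Grade 4 rate the rule stops somewhat more often, for example 0.061 instead of 0.026 at an assumed 10% Grade 4 plus 2% Grade 5. If the look has already been held, record how the count was made and whether any Grade 5 toxicity was left out.
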